3.2 Primary Objective

- To investigate the effects of a trimodal 8-week prehabilitation program on the return to function of patients undergoing RC as evaluated by functional outcome measures including the six-minute walk test (6MWT) and walking speed (10m walk test).

3.3 Secondary Objectives

- To investigate the impact and patient acceptability of a trimodal 8-week prehabilitation program on patient satisfaction and quality of life, as determined through questionnaires and patient interviews.
- To investigate the effects of a trimodal 8-week program on traditional outcomes including length of hospital stay, rates of morbidity, and return to oncological treatment
- To establish appropriate criteria that effectively identifies and triages those patients who would benefit most from prehabilitation, so that efficient health care service can be made accessible to those who need it most.
- To evaluate which functional outcome measures represent a valid index of recovery and are sensitive to change.

4 STUDY DESIGN

4.1 Study Overview

This is a single center, single-blind, pragmatic randomized-control trial. There will be a total of 50 (fifty) participants in the study. Each participant will be randomly enrolled into a prehabilitation or no-prehabilitation group at time of consent for RC and those in the intervention group will undergo 8 weeks of prehabilitation through the Total Cardiology program, hosted through the Repsol Centre. Each participant, independent of study group assignment, will receive the standard treatment as outlined in the Enhanced Recovery Protocol (ERP) for Radical Cystectomies (see Appendix 1). Those enrolled in the prehabilitation group will attend 2 supervised exercise-based sessions per week and will complete a home-exercise program three times per week (total 5 exercise sessions per week). In addition, they will receive 5 protein supplement drinks per week to consume after exercise, and will attend classes on nutrition and stress/anxiety reduction techniques. Measurements will be taken at baseline, 6 weeks (as a part of their regularly scheduled pre-admission clinic appointment), 8 weeks (just prior to surgery), 4 weeks post-op, and 8 weeks post-op.

Those patients enrolled in the no-prehabilitation group will receive a general, unsupervised, home-exercise program, information regarding good nutrition. They will be followed at their regularly scheduled appointments. Again, measurements will be taken at the same time intervals as the prehabilitation group.

Screening data will be reviewed to determine subject eligibility. Subjects who meet all inclusion criteria and none of the exclusion criteria will be entered into the study.

The following treatment groups will be established:

- Standard ERP + Trimodal Prehabilitation
- Standard ERP

Total duration of subject participation will be approximately sixteen weeks. Total duration of the study is expected to be approximately 1.5 years.

4.2 Population

Subjects with a diagnosis of bladder cancer, scheduled for elective bladder surgery, who meet the inclusion and exclusion criteria will be eligible for participation in this study.

4.3 Inclusion Criteria

1. Male or female \geq 18 years of age at time of consent for surgery.
2. Documentation of bladder cancer diagnosis as evidenced by diagnostic imaging and biopsy.
3. May or may not receive adjuvant therapy.
4. Written informed consent obtained from subject.

4.4 Exclusion Criteria

1. Presence of a condition or abnormality that in the opinion of the investigator would compromise the safety of the patient or the quality of the data. This includes:
 - a. ASA health class status 4-5;
 - b. Co-morbid medical, physical, and/or mental conditions including dementia, disabling orthopedic and neuromuscular disease, psychosis;
 - c. Severe cardiac abnormalities, end-stage organ disease, sepsis, or morbid obesity (BMI greater than 35);
2. Undergoing radical cystectomy for a reason other than bladder cancer.
3. Poor comprehension of English or French.
4. Screened* by Total Cardiology staff and determined to be not appropriate for prehabilitation at their facility.

* TC will conduct an exercise stress test on candidates with a moderate or high Framingham Index.

4.5 Total Number of Participants and Sample Size Justification

A total of 50 participants who meet the inclusion criteria and are willing to participate in the study will be enrolled, with 25 participants randomly allocated to each study treatment group. As this is a pilot study, we have funding for at most 25 participants to undergo prehabilitation.

4.6 Recruitment & Informed Consent

At RGH, patients diagnosed with bladder cancer and consent to surgery are operated on by [name], [name], [name], [name], [name], and [name]. A total of approximately 80 radical cystectomies are completed annually.

Patients will be screened by the medical team for health conditions that would prohibit participation in the program and those that are selected for prehabilitation will undergo further exercise testing at the Total Cardiology program to ensure participants are medically suitable for the intervention. The following are the steps taken for recruitment:

1. Patients who consent to elective bladder surgery that meet the inclusion/exclusion criteria will be identified and initial contact will be made by the physician assistant (RC case manager) at a scheduled appointment. The physician assistant will introduce the study to the patients.
2. If the patient decides they would like more information about the study and is willing to be contacted by the research study coordinator, the physician assistant will inform the study coordinator (JM).
3. The study coordinator (JM) will then contact the patient to explain all details of the study. If the patient is interested in participating, the coordinator will schedule a time to complete the informed consent (Appendix 5) and preoperative/baseline assessments at RGH. At this time, the patient will also be given the written informed consent to further read on their own time.
4. When the patient arrives for their scheduled appointment at RGH, they will be given all study details from the coordinator. Any further questions on their behalf will be addressed and they will be asked to sign the informed consent. Only participants who have capacity to provide fully informed consent themselves will be asked to sign a consent form.
5. Once informed consent is obtained, the patient will undergo their preoperative/baseline assessments as outlined later in this document.
6. Patient will be randomized into one of the two study groups and the study protocol will begin. Further physical and nutritional assessments will be conducted by a Physiotherapist and Registered Dietitian respectively.

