	
investigator would compromise the safety of the patient or adherence to the program. This includes:
 
 a. American Society of Anesthesiologists (ASA) health class status 4-5; b. Co-morbid medical, physical, and/or mental conditions including dementia, disabling orthopedic and neuromuscular disease, psychosis; c. Severe cardiac abnormalities, end-stage organ disease, sepsis, or morbid obesity (BMI greater than 35); 
 2. Undergoing radical cystectomy for a reason other than bladder cancer. 3. Poor comprehension of English or French 4. Screened by Total Cardiology staff and determined to be inappropriate for prehabilitation at their facility.
INTERVENTION / CONTROL GROUP	
Control: Radical cystectomy. Enhanced Recovery Protocol will be followed. Home exercise program & nutritional information provided.
 
Intervention: Trimodal prehabilitation received prior to radical cystectomy. Enhanced Recovery Protocol will be followed.

DURATION OF PARTICIPATION	16 weeks
EVALUATIONS	5 evaluation visits and 8 individual interviews conducted by a PaCER trained researcher.
STATISTICS Primary Analysis Plan	An available case analysis without imputation of missing values will be conducted. All analyses will be performed using Stata 14.1 (2015, StataCorp). All continuous variables will be reported as mean, 95% confidence interval. Categorical variables will be presented as frequency (%) and compared using Pearson's χ^2 test. A mixed effects model will be used to analyze repeated measures, including our primary outcome the 6MWT. A P-value <0.05 will be considered statistically significant.
Rationale for Number of Subjects	Funding is limited to \$15,000. This allows for a study of ~25 prehabilitation participants and 25 participants undergoing standard-of-care treatment.

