2.1 Risk / Benefit Analysis

2.1.1 Risk Assessment

Risks associated with an exercise program include minor aches and pains, potential for mechanical injuries, such as strains & sprains, and cardiovascular problems, such as heart arrhythmias, heart attack, or sudden cardiac arrest¹⁴. Participants undergo a medical evaluation by the Total Cardiology team to ensure participants are sufficiently healthy and medically stable to participate in a program. By tailoring the exercise programs to the individual needs of each participant, risks for mechanical injuries and exercise-associated complications are sought to be minimized. Participants are encouraged to take rests and keep physical activity within a moderate range to ensure safe participation in the program.

Typical risks associated with the use of oral nutrition supplements are rare, but include constipation, diarrhea, nausea and vomiting. Participants will undergo evaluation by a Registered Dietitian and will be monitored for adverse effects throughout the program. Pre-existing medical conditions such as diabetes may impact the ability to use nutritional supplements. These conditions will be reviewed by the Registered Dietitian and an appropriate personalized nutrition care plan will be developed in conjunction with the participant.

With respect to interviews, sharing personal experiences of surgery might make some patients uncomfortable. Participants will be advised to share only what they are comfortable with sharing. Participants will be informed that if at any time they experience feelings of anxiousness, sadness, or discomfort, they have the right to take a break during the interview, postpone the interview, or withdraw their consent to participate.

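### Failing the Total Cardiology screen is a whole-trial exclusion, but the protocol's steps provide that screen only for the prehabilitation arm, after randomisation

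*Protocol*

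**What the plan says.** **Passages that treat the screen as a condition of entry.** Section 4.4 lists as exclusion 4: "Screened* by Total Cardiology staff and determined to be not appropriate for prehabilitation at their facility". The synopsis carries the same criterion. The footnote in 4.4 adds: "TC will conduct an exercise stress test on candidates with a moderate or high Framingham Index". Section 4.1 says: "Subjects who meet all inclusion criteria and none of the exclusion criteria will be entered into the study". Step 1 of section 4.6 treats eligibility as known at first contact: "Patients who consent to elective bladder surgery that meet the inclusion/exclusion criteria will be identified".

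**Passages that treat it as clearance for the programme.** The paragraph before those steps says "those that are selected for prehabilitation will undergo further exercise testing at the Total Cardiology program". Section 2.1.1 says: "Participants undergo a medical evaluation by the Total Cardiology team to ensure participants are sufficiently healthy and medically stable to participate in a program". Section 6.3 places the Total Cardiology examination before the patient's prehabilitation programme starts.

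**Order of events.** Section 4.1 says: "Each participant will be randomly enrolled into a prehabilitation or no-prehabilitation group at time of consent for RC". Visit 1 (7.1) has consent at step 1, baseline measures next and randomisation at step 9. Total Cardiology is first mentioned at step 10, for those allocated to treatment. Steps 4 to 6 of section 4.6 follow the same order.

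**What happens on failure.** Nothing is stated. Section 8.1 allows study treatment to be stopped but does not say that follow-up continues. Its no-replacement rule covers only subjects who withdraw.

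**The concern.** An exclusion criterion protects a randomised comparison only if it is settled before allocation and in the same way for everyone. Here the criterion is written for the whole trial, but the only route by which it can be triggered runs through the prehabilitation arm after allocation. Staff facing a randomised patient who fails have a literal instruction that the patient is excluded and no instruction to the contrary.

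If they follow it, less fit patients leave one arm while their counterparts stay in the other. Where failing the screen goes with poorer recovery, the walk test and the clinical outcomes tilt toward prehabilitation even if it does nothing. The available-case analysis in 9.1 does not bring back a patient who has left. The prehabilitation arm could also fall below its planned 25.

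**Working it through.** **Step 1: can the passages be read consistently?** Section 5 requires consent before any study activity, so a screen done for the study cannot precede the consent visit. Between consent and randomisation, neither 4.6 nor 7.1 contains a screen. No passage sends a control patient to Total Cardiology. Step 10 of 7.1 uses *selected* for the result of randomisation, which supports reading the same word in 4.6 that way. A screen of everyone may have been intended, but no step delivers it.

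**Step 2: how often might it arise?** The documents give no failure rate, so this is a range of assumptions. With 25 patients and failure probability f, expected failures are 25f and the chance of at least one is 1 − (1 − f)^25.

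- f = 5%: 1.25 expected; chance of at least one 72%
- f = 10%: 2.5 expected; 93%
- f = 20%: 5 expected; 99.6%

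**Step 3: how far could the comparison shift?** There is no stated figure to reproduce, because the sample size is set by funding (9.2). The simulation has no true effect, 25 per arm and 300,000 trials per setting. The only documented input is the 64% complication rate from section 1.2. The assumptions are:

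- latent fitness L, with every variable below scaled to unit variance by adding independent noise e;
- baseline walk = √0.8·L + e and week-8 walk = √0.6·L + e, with an SD of 100 m;
- screen score = r·L + e, with r from 0.3 to 0.8;
- complication liability = −√0.25·L + e, cut at 64%;
- the k lowest screen scores of 25 removed from one arm only;
- ANCOVA on baseline standing in for the mixed model of 9.1.

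| k | Adjusted walk bias, m (r = 0.3 / 0.5 / 0.8) | Complication difference, points (r = 0.3 / 0.5 / 0.8) | ANCOVA rejection, r = 0.8 | Exact null size of χ² | χ² rejection, r = 0.8 |
|---|---|---|---|---|---|
| 1 | 0.4 / 0.6 / 1.0 | −0.5 / −0.7 / −1.1 | 5.0% | 4.86% | 4.91% |
| 2 | 0.7 / 1.2 / 1.9 | −0.8 / −1.3 / −2.0 | 5.1% | 5.67% | 6.16% |
| 3 | 1.0 / 1.7 / 2.9 | −1.2 / −1.9 / −2.9 | 5.2% | 4.95% | 5.42% |
| 5 | 1.6 / 2.7 / 4.6 | −1.9 / −3.0 / −4.8 | 5.5% | 4.86% | 6.28% |
| 7 | 2.2 / 3.6 / 6.2 | −2.5 / −4.2 / −6.6 | 5.8% | 5.45% | 8.04% |

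The exact null size is for the uncorrected test with 25 − k against 25 patients at 64%. With r = 0 the simulation reproduces these sizes.

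The walk bias is small because baseline adjustment removes 78 to 81% of the raw shift. An unadjusted χ² test on complications has no such protection. In the most extreme setting (k = 7, r = 0.8), changing the liability share from 0.25 to 0.10 or 0.40 gives −4.2 or −8.2 points and rejection of 6.5% or 9.5%. Length of stay and return to oncological treatment were not simulated.

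**Step 4: scale.** In this model the residual SD of the week-8 walk given baseline is 100·√(1 − 0.8 × 0.6) = 72.1 m. With 22 against 25 patients the standard error is 72.1·√(1/22 + 1/25) = 21.1 m. The largest bias at k = 3 is therefore 2.9/21.1 = 0.14 standard errors.

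**The case against.** The sentence in 4.6 stands before the numbered steps and begins with screening by the medical team, so the team could be doing the selecting. The 4.4 footnote speaks of candidates, which suggests people not yet entered. Section 2 says the hospital's recovery pathway already offers the programme, so a screen in routine care before study consent is possible. No passage says that a patient who fails leaves follow-up or analysis. Section 8.1 is about stopping prehabilitation, and the analysis set may be defined in a statistical analysis plan that is not shown. Reasons for failing at that facility may have nothing to do with walking capacity. The larger simulated figures need 5 to 7 of 25 to fail, which no document supports.

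Much of this stands as a limit on size and certainty: the harm is conditional, and with few failures it is small. Two other points also carry little weight. The rule in 7.2, which withdraws patients found unsuitable for surgery, applies to both arms and so is weak evidence of what would follow a failed screen. An arm falling below 25 is a risk of any attrition. The contradiction itself remains. If a screen of everyone before allocation was meant, 4.6 and 7.1 omit it and still need correcting. An analysis plan can say how to handle excluded patients, but it cannot settle when and in whom eligibility is assessed.

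**Conclusion.** The concern holds and should be fixed. The protocol contradicts itself on when criterion 4 is assessed and for whom, and a literal application would exclude patients from one arm after allocation.

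The size is unknown, because neither a failure rate nor a walk-test SD is documented. Under the stated assumptions, 1 to 3 failures leave the adjusted walk-test result almost untouched, and χ² rejection for complications exceeds its null size by at most 0.5 points. With 7 failures and r = 0.8, the excess is 8.04 − 5.45 = 2.59 points. The other exclusions and the medical team's own screen make many failures less likely. The direction favours prehabilitation only if failing predicts poorer recovery. Confidence is medium: the textual conflict is clear, but the consequence depends on conduct that the protocol leaves open.

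**What to change.** Reconcile 4.4, the synopsis, 4.6, 6.3 and 7.1. Under either option, who may exercise remains a clinical decision.

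**Option A, if the screen stays after randomisation.** Remove criterion 4 from 4.4 and the synopsis, and add to 4.6 and 8.1:

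> The Total Cardiology screen is not a study exclusion; it informs only the clinical decision whether the patient takes part in the programme. A randomised patient who does not pass stays in the study, is followed at the scheduled visits and is analysed in the allocated group.

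This is a wording amendment that uses visits already scheduled, and some clinical outcomes come from the hospital and registry records named in 10.1. Its price is dilution of about k/25 under a uniform effect: 4%, 12%, 20% or 28% for 1, 3, 5 or 7 failures.

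**Option B, if every candidate was meant to be screened.** State in 4.6, 6.3 and 7.1 that the screen takes place in all candidates after consent and before the envelope is opened. This avoids the dilution but needs more screens than the 25 that Option A requires. Randomising 50 who pass takes 50/(1 − f) screens, rounded up: 53, 57, 63 or 70 at failure rates of 4%, 12%, 20% or 28%. Against that stand about 80 cystectomies a year (4.6) and funding for at most 25 patients in prehabilitation (4.5). The cost per screen is not given, and randomisation would wait for the result.

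Option A is the cheaper of the two.

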5 RESEARCH METHODS AND PROCEDURES

Prior to conducting any study-related activities, written informed consent must be signed and dated by the subject.

5.1 Treatment Groups

Currently, RGH utilizes a newly developed, multidisciplinary Enhanced Recovery Protocol for all patients undergoing a radical cystectomy. At this time, all patients undergoing a radical cystectomy are following the ERP. For the purpose of this study, two treatment groups will be established:

5.1.1 RGH Enhanced Recovery Protocol; No Prehabilitation

Patients in this group will follow the standard ERP developed at RGH. See Appendix 1 for details of the ERP. This group will receive general instructions on post-operative exercises, expectations, and discharge planning by a physiotherapist at their pre-admission clinic appointment. Post-operatively, the patient will follow a standardized pathway as outlined in Appendix 1.

5.1.2 RGH Enhanced Recovery Protocol and Prehabilitation

Patients in this group will additionally follow a trimodal prehabilitation program consisting of a guided exercise program, nutritional supplementation, and stress reduction/anxiety reduction strategies.

5.2 Components of Trimodal Prehabilitation

5.2.1 Exercise Program

The exercise component will consist of approximately two 60 min sessions of supervised resistance and aerobic exercises. The sessions will be under the supervision of a kinesiologist and will take place in collaboration with the Total Cardiology group out of the Repsol Sport Centre. Each participant's program will be individualized based upon the baseline fitness test and will include:

- 5 min warm-up,
- 25 min of aerobic exercise (starting at 30-40% of heart rate reserve (HRR) and progressing to 50-60% HRR as tolerated by participant),
- 25 min of resistance training (6 exercises targeting major muscle groups performed at moderate intensity), and
- 5-10 min cool-down and stretching period.
- Clear explanations & demonstrations of program by the kinesiologist

In addition, patients will be asked to carry out a 60min aerobic-based exercise program at home (i.e. walking), unsupervised, 3 days/week, and complete incentive spirometry breathing exercises 3 times/day for 10 breaths. Incentive spirometry has been shown to have beneficial effects on post-operative outcomes¹⁹ and will be included for this reason. Participants will record these additional activities in a journal that is provided to them at the start of their program.

Training intensity progression will be advised by the kinesiologist when the participant can complete aerobic exercise with mild exertion and/or when the participant can complete 15 repetitions of a given resistance exercise.

The kinesiologist will follow all participants to assess program adherence (including unsupervised sessions documented in patient's journal) and to address any barriers that may prevent ongoing participation.

The control group will receive the regular radical cystectomy information and will be asked to complete a 60min aerobic-based home exercise program, unsupervised, 5 days/week, along with incentive spirometry breathing exercises 3 times/day for 10 breaths. This group will also record their activities in a journal and a member of the research team will check in by telephone weekly to assess adherence and address any barriers or questions the patient may have.

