1 INTRODUCTION

1.1 Abstract

A trimodal preoperative intervention known as prehabilitation (involving exercise, nutrition and psychological care) has been found to successfully improve functional recovery, an important patient-centered outcome, in colorectal surgery patients following the Enhanced Recovery After Surgery (ERAS) pathway. It is unknown whether the same program will be effective in patients undergoing surgery for bladder cancer (cystectomy). It is an opportune time to study prehabilitation at the Rockyview General Hospital given the recent roll-out of the Enhanced Recovery Protocol (ERP) for cystectomy patients and ongoing implementation of an integrated prehabilitation program.

Objective: To evaluate the appropriateness of a standardized prehabilitation program for implementation into an ERP for cystectomy patients and determine whether prehabilitation facilitates earlier recovery of functional capacity, as measured by six-minute walk test (6MWT)

Hypothesis: Prehabilitation will ultimately improve recovery of functional capacity, clinical and patient-centered outcomes in patients undergoing radical cystectomy for bladder cancer.

Design: A pragmatic randomized control trial of radical cystectomy patients following ERP and an 8-week trimodal prehabilitation program consisting of exercise therapy combined with nutritional counselling, protein supplementation, and psychological care will be compared to a cohort of patients following ERP care alone.

Main Outcome Measures: Return to preoperative functional walking capacity, as assessed using the validated six-minute walk test at the 8th postoperative week. All measures will be recorded at baseline, the day of surgery, and four and eight weeks after surgery. Traditional clinical outcome measures (e.g., length of hospital stay) will also be evaluated. Finally, patient interviews will be conducted to evaluate the appropriateness of prehabilitation.

Conclusion: The proposal will provide insight into the feasibility and effectiveness of trimodal prehabilitation for radical cystectomy patients and ultimately lead to improved clinical outcomes and reduced morbidity.

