2.1.2 Benefit Assessment

Generally speaking, the benefits associated with exercise and good nutritional intake, far outweigh the risks. Exercise has been linked to improving the status of many physical and mental conditions including cardiovascular disease, mental health, obesity, diabetes, and chronic pain and has been shown to improve cardiovascular function by optimizing the ventilation/perfusion

of the lungs and improving the cardiac output of the heart¹⁵. As the purpose of this study is to observe how side effects associated with surgical stress may be attenuated, the benefits of these interventions will become clearer. Given the large number of positive effects of exercise and good nutrition, it is hoped these initiatives will facilitate the recovery process and reduce impact to a person's functional status, thereby improving quality of life.

In view of the impact of cancer on physical, nutritional and psychological status, it is necessary to optimize body reserves preoperatively to prepare the patient for the stress of surgery. This study could provide some direction to guide clinicians in optimizing the perioperative period in patients undergoing bladder surgery as well as contributing to our understanding of which outcome measures represent a valid index of recovery and are sensitive to changes.

Finally, by conducting individual interviews, participants will have a direct impact on how prehabilitation is carried out in the future. They will have the opportunity to shape the program and ensure it is in accordance with their capabilities and beliefs. It should also be mentioned that this study has the potential to affect organizational change within Alberta Health Services by providing the groundwork research for which future health care management decisions can be made in an evidence-based manner.

This said, it is not immediately clear that prehabilitation will lead to the proposed functional benefits and our team is acutely aware of additional costs associated with such a program (i.e. facility & protein supplement costs). Benefits for participants are best contrasted with a control group following the standard of care and a basic home exercise program and can allow for better decision making from an organizational level.

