3 STUDY OBJECTIVES

3.1 Research Question

Does an 8-week trimodal prehabilitation program consisting of exercise therapy combined with nutritional counseling, protein supplementation, and psychological care of patients undergoing radical cystectomy improve postoperative functional and quality of life (QOL) outcomes compared to patients who follow ERP care alone?

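### The research question names ERP alone as the comparator, but controls are prescribed a 60-minute home aerobic programme five days a week, so the trial cannot answer the question as worded

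*Protocol*

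**What the plan says.** The Protocol describes the control arm in two ways.

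**As ERP alone**
- 1.1 (Abstract, design statement): the prehabilitation programme "will be compared to a cohort of patients following ERP care alone".
- 3.1 (Research Question): asks about "outcomes compared to patients who follow ERP care alone".
- 4.1 (arm list): one arm is "Standard ERP + Trimodal Prehabilitation"; the other is labelled as standard ERP with nothing added.
- 5.1.1 (control arm): "This group will receive general instructions on post-operative exercises, expectations, and discharge planning by a physiotherapist". No exercise before surgery is mentioned.

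**As ERP plus home exercise**
- Synopsis: the control entry adds a home exercise programme and nutrition information to the ERP.
- 2.1.2: "Benefits for participants are best contrasted with a control group following the standard of care and a basic home exercise program".
- 4.1 (body text): "Those patients enrolled in the no-prehabilitation group will receive a general, unsupervised, home-exercise program".
- 7.1: controls are given the home programme and nutrition information at Visit 1.
- 5.2.1: the control group "will be asked to complete a 60min aerobic-based home exercise program, unsupervised, 5 days/week". It also receives incentive spirometry three times daily for 10 breaths, a journal, and a weekly call from the research team about adherence and barriers.

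The dose appears only in 5.2.1, which sits under the heading for the components of trimodal prehabilitation.

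**The concern.** The two descriptions cannot both define the comparator. The primary objective in 3.2 names no comparator, and neither do the secondary objectives in 3.3. Within the objectives section, 3.1 alone says what prehabilitation is compared with, and what it says is not what controls receive.

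The comparator fixes what the result means. A null six-minute walk result would mean no demonstrated benefit of the package over this home programme. Read through 3.1, it would be reported as no demonstrated benefit over ERP alone, which the trial does not test. A positive result would favour the package over an active control, which is also a different statement from the one 3.1 invites. Section 2 intends the results to refine the local programme and to support multi-site studies, and 2.1.2 intends them to inform organisational decisions. A mislabelled contrast would carry into all of these.

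**Working it through.** **Inputs (prescribed amounts)**
- Prehabilitation: 2 supervised and 3 home sessions a week (4.1). Section 5.2.1 does not say that the two supervised sessions are weekly; 4.1 supplies this.
- Supervised session (5.2.1): 5 min warm-up, 25 min aerobic, 25 min resistance, 5–10 min cool-down.
- Prehabilitation home session (5.2.1): 60 min.
- Control (5.2.1): 60 min at home, 5 days a week.
- Spirometry (5.2.1): 3 times a day, 10 breaths, in both arms.

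**The plan's own figure.** Section 4.1 gives "total 5 exercise sessions per week" for prehabilitation: 2 + 3 = 5. It reproduces.

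**Supervised session length.** 5 + 25 + 25 + 5 = 60 min, to 5 + 25 + 25 + 10 = 65 min.

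**Weekly prescription**

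| | Prehabilitation | Control |
|---|---|---|
| Sessions | 2 + 3 = 5 | 5 |
| Total minutes | 2×60 + 3×60 = 300, to 2×65 + 3×60 = 310 | 5×60 = 300 |
| Supervised sessions | 2 | 0 |
| Resistance minutes | 2×25 = 50 | 0 |
| Spirometry, breaths per day | 3×10 = 30 | 3×10 = 30 |

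**Over 8 weeks**, assuming controls exercise from Visit 1 until surgery:
- Sessions: 5×8 = 40 in each arm.
- Minutes: 300×8 = 2400 to 310×8 = 2480, against 300×8 = 2400.
- Supervised sessions: 2×8 = 16 against 0.
- Control telephone calls: about 1×8 = 8.

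**What differs by prescription.** Sessions match and total time is about equal. What separates the arms is supervision and individual progression, resistance work, the protein supplement, dietitian access on supervised days, and the anxiety-reduction class. That is a comparison of a package with an active exercise control.

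**Could ERP alone be read to include the home programme?** Section 2.1.2 lists standard care and the home programme as two items. The synopsis and the 4.1 body text also state the programme separately from the ERP. Section 5.1.1 describes ERP care without exercise before surgery. Taken together, the programme is an addition to the ERP.

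**The case against.** **The home programme is disclosed.** It is. The synopsis, 2.1.2, 4.1, 5.2.1 and 7.1 all mention it, and 2.1.2 gives a reason for it. Staff working from sections 4, 5 and 7 would deliver the right control. So a reader who inferred a hidden or accidental control intervention would be wrong. What remains is that disclosure elsewhere does not make the comparator in 1.1 and 3.1 correct.

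**The ERP might already contain it.** Appendix 1 is not shown, and section 2 says the local ERP includes an optional 8-week prehabilitation programme. The milder reading cannot be excluded outright. The three places that list the home programme separately make it the less likely one.

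**Completed exercise may differ.** This stands. Prehabilitation has supervised sessions with recorded attendance; controls exercise unsupervised with a weekly call. A reader might infer that a positive result could not be due to more exercise. The documents support this only for prescribed sessions and time, not for exercise actually done.

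**Aerobic dose.** A reader might also infer that controls are prescribed more aerobic work, since 2×25 + 3×60 = 230 min a week is less than 300. That counts every home minute as aerobic. The make-up of a home session is not given, and a heart-rate-reserve target is set only for the supervised aerobic block, so no ranking of aerobic dose is secure. The point does not need one.

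**This is a pilot.** With 25 per arm set by funding and no power calculation (4.5, 9.2), a null result could not establish absence of benefit against any comparator. That is true, but it does not correct which comparator the result refers to.

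**Conclusion.** The point holds as a mismatch between the stated research question and the contrast under test. Sections 1.1 and 3.1, the 4.1 label and 5.1.1 describe ERP without exercise before surgery. The synopsis, 2.1.2, the 4.1 body text, 5.2.1 and 7.1 give controls home exercise, at a prescribed load about equal to the intervention arm's: 5 against 5 sessions and 300–310 against 300 min a week. The trial can say whether the supervised trimodal package adds to that active control. It cannot answer 3.1 as worded.

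This rests on prescribed amounts, not adherence, and on reading the home programme as additional to an ERP whose appendix is not shown. It does not imply that the control arm is badly chosen. The wording should be corrected because it changes what may be concluded; it raises no safety concern.

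**What to change.** In 1.1, 3.1, 5.1.1 and the 4.1 arm label, state the comparator as: ERP plus an unsupervised 60-minute aerobic home programme on 5 days a week, incentive spirometry 3 times a day, nutrition information, an activity journal and weekly telephone calls. Spirometry and nutrition information need to be named, since controls receive both and leaving them out would give another incomplete description. Limit the conclusion to the trimodal package against that control.

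The control programme, allocation, visits, outcomes, sample size and budget do not change. The costs are a narrower claim, since the trial can no longer be presented as a test against ERP alone, and a routine modification submitted to the ethics board with its application record updated (11.3).
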